11.1 ADVERSE EVENTS

Adverse events will be coded by SOC and preferred term using the Medical Dictionary for Regulatory Activities.

For a given AE and patient, if more than 1 severity grade is reported, the worst severity grade (the greater of the onset and maximum severity recorded on the electronic case report from [eCRF]), will be used for analysis.

Adverse events will be classified into ocular AEs and nonocular AEs. An ocular AE will be determined as indicated on the AE form of eCRF, and thus are not limited to AEs with primary SOC of eyes. The treatment-related ocular AEs will be further broken down by either related to injection procedure or related to study drug as indicated on eCRF. Ocular AEs will be tabulated by treatment group for the study eye and pooled for the fellow eye, and nonocular AEs will be summarized by treatment group for patient. Analysis by cycle of treatment will also be performed.

Treatment-Emergent Adverse Events

An AE will be considered a treatment-emergent adverse event (TEAE) for the study treatment period if the AE meets 1 of the following criteria:

- The onset date is on or after the first study treatment date.
- The onset date is before the first study treatment date and either:
 - The severity of the event worsened on or after the first treatment date.
 - The event became serious on or after the first study treatment date.

An AE will be considered as a TEAE for a treatment cycle if the AE meets 1 of the following criteria:

- The onset date is on or after the treatment administration of the cycle but prior to the next cycle administration.
- The onset date is before the treatment administration of the cycle and either:
 - The severity of the event worsened on or after the treatment administration of the cycle.
 - The event became serious on or after the treatment administration of the cycle.

Overall summary of TEAEs will be provided on a per-patient basis for categories of all TEAEs, treatment-related TEAEs, injection procedure-related TEAEs, study drug-related TEAEs, serious TEAEs (STEAEs), deaths, and TEAEs leading to study discontinuation. Each category (except deaths) will be further classified into ocular and nonocular subcategories.

The number and percentage of patients reporting TEAEs will be provided on a per-patient basis by 1) SOC and preferred term; 2) SOC, preferred term and severity in descending order of frequency for each treatment group.

The number and percentage of patients reporting nonocular TEAEs in each treatment group will be tabulated by SOC and preferred term. Also the number and percentage of patients reporting treatment-related (including study drug related or injection procedure related) nonocular TEAEs in each treatment group will be tabulated by SOC and preferred term.

Similar analyses will be done for ocular TEAEs including 1) by PT and severity; 2) treatment-related TEAEs by PT for each treatment group by study eye and fellow eye. In addition, similar analyses will be performed for ocular TEAEs by treatment cycle.

Within each treatment cycle, ocular TEAEs identified (onset or worsened) within 2 days of administration and identified more than 2 days of administration of each cycle will be summarized by each treatment group for study eye and pooled for fellow eye.

Serious TEAEs

Nonocular and ocular STEAEs will be summarized by preferred term and treatment group, respectively.

TEAEs Leading to Study Discontinuation

Nonocular TEAEs and ocular TEAEs leading to premature discontinuation of the study will be summarized by preferred term and treatment, respectively.

Similarly, ocular TEAEs leading to premature discontinuation will also be tabulated by treatment group by treatment cycle.

Ocular TEAEs Leading to Study Drug Discontinuation or Regimen Change

Ocular TEAEs leading to study drug discontinuation will be summarized by preferred term and treatment for the entire study period and also for each cycle. Ocular TEAEs leading to study drug discontinuation or regimen change are defined as the ocular TEAEs with action regarding study drug reported as “Discontinued” or “Regimen Changed” on the eCRF AE form.

Ocular TEAEs Leading to Implant Removal

Ocular TEAEs leading to implant removal will be summarized by preferred term and treatment for the entire study period and also for each cycle.

[REDACTED]

[REDACTED]

[REDACTED]

[REDACTED]

[REDACTED]

[REDACTED]

[REDACTED]

[REDACTED]

[REDACTED]

[REDACTED]

[REDACTED]

[REDACTED]

[REDACTED]

[REDACTED]

[REDACTED]

[REDACTED]

[REDACTED]

[REDACTED]

[REDACTED]

[REDACTED]

[REDACTED]

[REDACTED]

[REDACTED]

[REDACTED]

[REDACTED]

[REDACTED]

[REDACTED]

[REDACTED]

[REDACTED]

[REDACTED]

[REDACTED]

[REDACTED]

[REDACTED]

[REDACTED]

[REDACTED]

[REDACTED]

[REDACTED]

[REDACTED]

[REDACTED]

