11.0 SAFETY ANALYSES

The safety analysis will be performed using the safety population. The safety parameters will include the following nonocular safety parameters: nonocular AEs, clinical laboratory values, vital signs, and pregnancy; [REDACTED]

[REDACTED] Unless otherwise stated, the last nonmissing safety assessment before the first dose of study treatment will be used as the baseline for all analyses of that safety parameter. Continuous variables will be summarized by number of patients and mean, SD, median, the 1st quartile and the 3rd quartile, minimum, and maximum values. Categorical variables will be summarized by number and percentage of patients.

[REDACTED]

For all safety by-cycle summary analyses, in order to compare cycles of similar duration, the data included in each cycle will be,

- Cycle 1 (16 weeks): data from the 1st injection to the 2nd injection date -1 or upper bound of week 15 visit window (section 16.1) if a patient didn't receive the 2nd injection;
- Cycle 2 (16 weeks): data from the 2nd injection to the 3rd injection date -1 or upper bound of week 31 visit window (section 16.1) if a patient didn't receive the 3rd injection;
- Cycle 3 (20 weeks): data from the 3rd injection to upper bound of week 52 visit window (section 16.1);
- Extended safety follow up: data after week 52 for patients with 3 injections and extended follow up.

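### As written, SAP 11.1 puts an ocular event's later, worse grade into the Cycle 1 severity table, which does not fit the Cycle 1 data cut-off in SAP 11.0

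*SAP*

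**What the plan says.** Three parts of the SAP bear on this point.

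**Severity (SAP 11.1).** When more than one grade is reported for a patient's event, the analysis uses "the worst severity grade (the greater of the onset and maximum severity recorded on the electronic case report from [eCRF". The sentence mentions neither cycles nor dates.

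**By-cycle tables (SAP 11.1).** The section states that "Analysis by cycle of treatment will also be performed". For ocular events it says "Similar analyses will be done for ocular TEAEs including 1) by PT and severity", and it closes that paragraph with "In addition, similar analyses will be performed for ocular TEAEs by treatment cycle". An event belongs to a cycle if "The onset date is on or after the treatment administration of the cycle but prior to the next cycle administration". An event that began earlier also belongs to a cycle if "The severity of the event worsened on or after the treatment administration of the cycle". No separate severity rule is given for the by-cycle tables.

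**Cycle windows (SAP 11.0).** The windows are introduced with "For all safety by-cycle summary analyses, in order to compare cycles of similar duration, the data included in each cycle will be". Cycle 1 is then defined as "data from the 1st injection to the 2nd injection date -1", with the upper bound of the Week 15 visit window as the end for a patient who has no second injection.

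**The concern.** The safety hypothesis (Protocol 2.2, SAP 5.0) is that the profile is acceptable after single and after repeat administration. For ocular events, the by-cycle severity table is where a reader would look to see whether events are graded worse after a second or third implant than after the first.

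That comparison needs the Cycle 1 column to hold only what was seen before the second administration. A single per-event maximum does not ensure this. An event with onset in Cycle 1 keeps its place there by its onset date but takes a grade that it may have reached only after a later administration. Cycle 1, the single-administration period, then looks more severe than it was, and the step up from Cycle 1 to the later cycle looks smaller.

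**Working it through.** No figure in the plan is at issue, so the check is a trace of one event through the rules.

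**Test event.** An ocular adverse event starts as mild after the first injection, is still open at the second, and becomes severe after the second.

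**Step 1: which cycles list it?** Its onset lies between the first and second administrations, so the onset criterion in 11.1 makes it a Cycle 1 event. It then worsened after the second administration, so the worsening criterion makes it a Cycle 2 event too. It is listed in both.

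**Step 2: which grade does it carry?** Under the 11.1 severity rule the grade is the greater of onset (mild) and maximum (severe), hence severe. Nothing in the rule varies this by cycle.

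**Step 3: compare with 11.0.** If the 11.0 window also limits the grade, Cycle 1 can use only data up to the day before the second injection, and the worst grade in that period is mild.

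| Table | 11.1 rule as written | 11.0 window also applied to the grade |
|---|---|---|
| Cycle 1 | severe | mild |
| Cycle 2 | severe | severe |
| Whole study | severe | severe |

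The two sections give different answers in one cell only, Cycle 1.

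**Step 4: which tables are touched?** Only by-cycle tables that display severity. From the visible text that means ocular events by preferred term and severity, repeated by cycle. No by-cycle severity table is named for nonocular events. Incidence by preferred term and the tables for relatedness, discontinuation and implant removal do not use the grade.

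**Step 5: can a size be given?** The number of events misgraded in Cycle 1 equals the number of ocular events that start in Cycle 1, are still open at the second administration, and worsen after it. The documents give no rate for any of these conditions, so no number follows.

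**The case against.** The strongest reply is that 11.0 already settles the matter. Its windows are stated for every by-cycle safety summary, and a grade first reached after the second injection is not Cycle 1 data. On that view 11.1 picks the worst grade among the data admitted to the cycle, and the two sections agree. This reading is open, and for that reason it would go too far to say that the SAP states a rule of using the worst grade ever recorded in by-cycle tables. But nothing says that the window limits the grade, and 11.1 names a specific source, the maximum on the eCRF. Section 11.1 does not otherwise follow the 11.0 windows either: for a patient without a second injection, 11.0 closes Cycle 1 at the upper bound of the Week 15 window, while the onset criterion in 11.1 has no such end. A programmer following 11.1 would use the maximum.

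Four other objections limit the point.

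- **Not hidden.** A reader might infer that worsening with repeat implants is moved out of the later cycle or concealed. It is not. The event is counted again where it worsens, and 11.1 also summarizes ocular events with onset or worsening within, and beyond, 2 days of each administration. What suffers is the contrast between cycles.
- **By-cycle severity table inferred.** The SAP plans analyses by cycle similar to the ocular ones, without naming severity again. SAP 4.0 places table specifications in a separate document that is not available here, and a cycle-specific derivation could be there.
- **Probably few events.** Protocol 1.3.3 reports that most events in the Phase 1/2 study were mild or moderate and occurred within the first 2 days. Protocol 5.10 allows readministration to be withheld because of earlier adverse events or safety concerns. Both suggest that long-open events that worsen after another implant would be uncommon, though neither gives a rate.
- **Data may be limited.** The eCRF layout is not shown. If each worsening is entered as a new record with its own start date, the problem shrinks, although a field for maximum severity suggests one record per event. If only onset and maximum grades are stored, intermediate grades may be lost.

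**Conclusion.** The point stands in a limited form. Followed as written, the 11.1 severity rule gives a wrong Cycle 1 grade to any ocular event that starts in Cycle 1 and worsens after a later administration, and this is inconsistent with the 11.0 cut-off. The effect runs one way: Cycle 1 severity is overstated, and the difference between single and repeat administration is diluted.

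The conclusion rests on two assumptions: that the by-cycle repeat of the ocular analyses includes preferred term by severity, and that one eCRF record holds both onset and maximum severity. The scope is descriptive safety tables; no hypothesis test or efficacy conclusion depends on them.

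A reader might want to attach a percentage of eyes shown as severe in error. The documents do not support any such figure.

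**What to change.** Add to SAP 11.1, after the severity rule: *For by-cycle tables that show severity, the grade is the worst grade reached within that cycle's window as defined in Section 11.0. Whole-study tables use the overall maximum.*

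If the eCRF holds only onset severity, maximum severity and a date of worsening, state the fallback: when the worsening date falls in a later cycle, use the onset grade in the onset cycle and the maximum grade in the cycle where the event worsened.

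The date of worsening should not be a new requirement, since both the by-cycle event definition and the 2-day summary in 11.1 already depend on it. The cost is the added text and a derivation change. There is one small downside: for an event that worsens more than once, for example mild to moderate in Cycle 1 and then severe in Cycle 2, the fallback would show mild in Cycle 1 because the intermediate grade may not be recoverable. A footnote to the table can say so.

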Study Compound: Bimatoprost sustained-release (SR) biodegradable implants containing preservative-free AGN-192024 (bimatoprost)

Phase: 3

Study Objectives:

To evaluate the intraocular pressure (IOP)-lowering efficacy and safety of 2 dose strengths of Bimatoprost SR in patients with open-angle glaucoma (OAG) or ocular hypertension (OHT) after initial and repeated administrations

Clinical Hypotheses:

At least 1 dose strength (10 µg or 15 µg) of Bimatoprost SR will have an IOP-lowering effect that is noninferior to that of topically administered timolol maleate 0.5% (hereafter referred to as timolol) eye drops in patients with OAG or OHT following single and repeat administration.

Bimatoprost SR administered intracamerally in dose strengths of 10 µg or 15 µg will have an acceptable safety profile in patients with OAG or OHT following single and repeat administration.

Study Design

Structure: Phase 3, multicenter, randomized, masked, parallel-group comparison (2 dose strengths of Bimatoprost SR versus active control), repeat administration

Duration: Approximately 22 months, consisting of screening of up to 28 days before washout, washout period of up to 42 days before initial administration of study medication, 52-week treatment period, plus 8 months extended follow-up

Study Treatment Groups: Bimatoprost SR dose groups: 10 µg and 15 µg

Control: Timolol eye drops plus Sham needleless procedure (that involves touching the eye at the area of insertion with a needleless applicator).

Dosage/Dose Regimen: Patients will receive 1 of 2 dose strengths of Bimatoprost SR or Control treatment in the study eye on Day 1 (with repeat administration of the same dose strength or Sham at Week 16 and Week 32).

Bimatoprost SR-treated patients will receive intracameral administration of Bimatoprost SR in the study eye using a prefilled applicator. Timolol vehicle eye drops will be used twice daily (BID; in the morning and evening) to mask the treatment of patients receiving Bimatoprost SR in the study eye. The fellow eye will receive a Sham needleless procedure (hereafter called Sham administration or Sham administration procedure) plus topical timolol eye drops, BID. Control group patients will receive a Sham administration plus timolol in both eyes.

All patients will be masked to their treatment group. Treatment groups are shown in Table 1.

Table 1 Treatment Groups

Treatment	Study Eye Treatment	Fellow Eye Treatment

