5.6.1 Treatment Regimen/Dosage Adjustments

Patients who have received nonstudy topical IOP-lowering medication (prohibited before Week 52 unless required for safety reasons due to inadequate IOP control and attested to by the investigator) in a Bimatoprost SR study eye will receive Sham administration in that eye on the Bimatoprost SR repeat administration day(s). Patients who have received nonstudy topical IOP-lowering medication in a fellow eye or a Control Group study eye will continue to receive Sham administration in that eye on the administration day(s).

Patients who have received nonstudy IOP-lowering medication in both eyes will not undergo Bimatoprost SR administration or Sham administration in either eye.

Patients who use nonstudy IOP-lowering medication (prohibited before Week 52 unless required for safety reasons due to inadequate IOP control and attested to by the investigator) in only one eye will be followed for the duration of the study. If used in both eyes, patients will be followed at minimum for 12 months after the last administration of Bimatoprost SR or Sham. Patients using nonstudy IOP-lowering medications in both eyes prior to the Week 16 or Week 32 Administration Day will not attend the administration visit(s), nor will they attend the Day 2, Days 4 and 8 (phone call), or 2-week visits (ie, Weeks 2, 18, and 34) following an administration. They would continue the schedule at Week 22 or Week 38, as appropriate for the administration cycle.

Patients who have received nonstudy IOP-lowering medication in both eyes before the time of the Month 14 visit are not required to attend the Month 14 or 18 visits unless the visit is 12 months after their last injection or Sham, at which time the patient may exit early and should complete all Month 20/Exit visit examinations. Patients who have received nonstudy IOP-lowering medication in both eyes by the time of the Month 16 visit are not required to attend the Month 18 visit, unless that visit is 12 months after their last injection or Sham, at which time the patient may exit early and should complete all Month 20/Exit visit examinations.

For patients who have not received nonstudy IOP-lowering medications by the time of study discontinuation or completion, poststudy evaluations regarding the need for IOP-lowering medications should be conducted according to the treating physician's clinical opinion.

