7.3.4 Safety Analyses

The Medical Dictionary for Regulatory Activities (MedDRA) nomenclature will be used to code adverse events. Adverse events will be coded from the verbatim text into preferred term and system organ class (SOC). The number and percent of patients reporting treatment emergent adverse events will be tabulated based on the primary SOC and preferred terms. Summary tables will be generated for all adverse events regardless of causality as well as treatment-related adverse events for the entire study and by treatment cycle.

Other safety variables include vital signs (blood pressure, pulse rate, and temperature) and pregnancy test results. [REDACTED]

[REDACTED]

[REDACTED]

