8.8 Early Discontinuation of Patients

Patients may voluntarily withdraw from the study at any time.

Patients who have received nonstudy IOP-lowering medication in only one eye will be followed for the duration of the study through the Month 20 visit.

Patients who have received nonstudy IOP-lowering medication in both eyes, or who do not complete an Administration Day visit, may discontinue the study 12 months after the last Bimatoprost SR or Sham administration at which time they should complete the Month 20/Exit visit procedures.

Notification of early patient discontinuation from the study and the reason for discontinuation will be made to the sponsor and will be clearly documented on the appropriate eCRF.

When patients exit before Month 20, the site should complete all procedures for the Month 20/Exit visit at the patient's last visit.

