Prior and concomitant medications will be separately summarized using the safety population for each treatment group as the number and percentage of patients under each indication preferred term (MedDRA) and unique base preferred name from the World Health Organization Drug Dictionary Enhanced (WHODDE).

Concurrent procedures will be provided in the listings.

Non-study IOP Lowering Medications/Procedures

A non-study IOP-lowering medication is defined as a medication for which the investigator specifically marked “Yes” to the question “Is this medication used as a non-study IOP-lowering medication?” on the concomitant medication electronic case report from (eCRF). A non-study IOP-lowering procedure is defined as a procedure for which the investigator specifically marked “Yes” to the question “Was this an IOP-lowering procedure?” on the concurrent procedure eCRF.

Other medications or procedures that could potentially reduce IOP but are not marked in the eCRF as non-study IOP-lowering medications/procedures will be listed in the separate document used to identify data excluded from the PP analysis.

Washout Ocular Medication

Similarly, washout ocular medications will be tabulated by treatment group for the study eye and pooled for the fellow eye.

9.0 **EXTENT OF EXPOSURE AND TREATMENT COMPLIANCE**

9.1 **EXTENT OF EXPOSURE**

Throughout the study, each patient will receive up to 3 administrations of Bimatoprost SR or Sham injection in each eye with a fixed interval of 16 weeks. The number and percentage of patients receiving Bimatoprost SR or Sham treatment in the study eye during the study will be tabulated by the number of treatment administrations for each treatment group.

Each patient's study duration will be calculated as the number of days between the exit date and Day 1 Administration Day, inclusively (date of the exit - Day 1 Administration date + 1). Patients' study duration will be summarized using descriptive statistics for each treatment group.

10.0 **EFFICACY ANALYSES**

The primary efficacy variable for country/regions other than US will be time-matched IOP change from baseline in the study eye. The primary efficacy variable for the United States (US) Food and Drug Administration (FDA) (Division of Transplant and Ophthalmology Products) is IOP in the study eye (Section 10.3.1).

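### Follow-up after Week 52 can end early because of events after randomisation, yet whole-study adverse events are tabulated as crude percentages with no time at risk

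*SAP*

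**What the plan says.** **Planned follow-up.** The Protocol Summary sets a "52-week treatment period, plus 8 months extended follow-up", which is about Month 20.

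**Early exit.** Protocol 8.8 covers patients given nonstudy IOP-lowering medication (rescue, below) bilaterally, "or who do not complete an Administration Day visit, may discontinue the study 12 months after the last Bimatoprost SR or Sham administration". Protocol 8.9 repeats the 12-month rule. Rescue in one eye does not shorten follow-up: under 8.8 those patients stay to Month 20.

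**Reduced visits.** Under Protocol 5.6.1, patients rescued in both eyes before Month 14 "are not required to attend the Month 14 or 18 visits unless the visit is 12 months after their last injection or Sham".

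**Tabulation.** Protocol 7.3.4 plans: "Summary tables will be generated for all adverse events regardless of causality as well as treatment-related adverse events for the entire study". SAP 11.1 specifies: "The number and percentage of patients reporting TEAEs will be provided on a per-patient basis by 1) SOC and preferred term". The denominator is the safety population (everyone treated, SAP 6.2), and the whole-study TEAE definition has no upper time limit. SAP 9.1 says each patient's "study duration will be calculated as the number of days between the exit date and Day 1 Administration Day, inclusively", but this is only described by group and is not used as a denominator.

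**By-cycle tables.** SAP 11.0 defines windows so that cycles of similar length are compared. Cycles 1 and 2 are cut at the Week 15 and Week 31 visit windows when the next injection is not given. The extended follow-up period is limited to patients who had three injections.

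**The concern.** A crude percentage is a fair estimate of risk to a fixed time only if nearly everyone is observed to that time. Up to Week 52 this is so for patients who stay in, because the earliest permitted exit is about Week 52. After Week 52, length of observation depends on rescue in both eyes and on whether redosing took place, and both can be related to treatment and to earlier adverse events.

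The by-cycle tables do not fill the gap. In a patient who was not redosed, an event after the truncated cycle window, or after Week 52, belongs to no defined by-cycle period. It is visible only in the whole-study table, where follow-up length is ignored.

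At stake is the description of late safety after repeat administration, which is part of the trial's safety hypothesis.

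**Working it through.** The documents state no figure on this point. Their overall duration does reproduce: 28/30.44 + 42/30.44 + 52/4.348 + 8 = 0.92 + 1.38 + 11.96 + 8 = 22.3 months, against a stated 22 or so.

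**Step 1. Earliest permitted exit.** Administrations are at Day 1, Week 16 and Week 32 (Protocol 5.6). With 4.348 weeks per month, exit month = (week of last administration)/4.348 + 12.

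| Administrations | Earliest exit | Months seen after Week 52 |
|---|---|---|
| 1 | 0 + 12 = 12.0 | 0 |
| 2 | 3.7 + 12 = 15.7 | 3.7 |
| 3 | 7.4 + 12 = 19.4 | 7.4 (taken below as the full 8) |

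**Step 2. Shortfall within one arm.** The following are assumptions, because the documents give no exit, rescue or redosing rates and no late event risk:
- share a leaves after one administration and share b after two, each at the earliest date;
- the hazard is constant over the 8 months from Week 52 to Month 20;
- exit is unrelated to risk;
- p is the true 8-month risk.

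Crude risk = b × [1 − (1 − p)^(3.7/8)] + (1 − a − b) × p.

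For p = 5%, the bracket is 1 − 0.95^0.4625 = 2.34%.

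| a, b | Crude risk | Crude/true |
|---|---|---|
| 5%, 5% | 0.05 × 2.34 + 0.90 × 5 = 4.62% | 0.92 |
| 10%, 20% | 0.20 × 2.34 + 0.70 × 5 = 3.97% | 0.79 |
| 20%, 20% | 0.20 × 2.34 + 0.60 × 5 = 3.47% | 0.69 |

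The ratios hardly change at p = 2% or 10%. With 200 patients per arm and p = 5%, the first row misses 0.8 patients with an event and the last row 3.1.

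**Step 3. Between arms.** The same formula, with exit shares written as a + b:

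| True risk, implant v control | Exits, implant v control | Crude risk, implant v control | Crude ratio | True ratio |
|---|---|---|---|---|
| 5% v 5% | 10+20% v 5+5% | 3.97% v 4.62% | 0.86 | 1.00 |
| 5% v 5% | 5+5% v 10+20% | 4.62% v 3.97% | 1.16 | 1.00 |
| 10% v 5% | 10+20% v 5+5% | 7.95% v 4.62% | 1.72 | 2.00 |
| 10% v 5% | 10+10% v 10+10% | 8.48% v 4.23% | 2.00 | 2.00 |
| 10% v 5% | 5+5% v 10+20% | 9.24% v 3.97% | 2.33 | 2.00 |

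The ratio is shrunk, unchanged or inflated according to which arm loses more patients.

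**Step 4. Would one whole-study patient-year rate be enough?** Take a = b = 20%. Mean follow-up is 0.20 × 12 + 0.20 × 15.7 + 0.60 × 20 = 17.5 months, so dividing by patient-time scales the crude figure by 20/17.54 = 1.14.
- Event arising only after Week 52: 0.69 × 1.14 = 0.79 of the truth, still short.
- Event clustered at administration, so already fully observed: 1.14 times the truth, overcorrected.
- Rate confined to Week 52 to Month 20: mean time observed is (0.20 × 3.7 + 0.60 × 8)/8 = 0.69 of the period, and 0.69/0.69 = 1.00.

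Only the period-specific rate recovers the late risk.

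**The case against.** A reader might infer that the crude tables favour Bimatoprost SR. The documents do not support that. The exit rules are identical in all arms, and no rates by arm are given. There is a plausible route to more early exit in the implant arms, because Protocol 5.10 lets redosing be withheld for earlier adverse events. It remains a possibility. Wear-off of the implant in the study eye alone leads to one-eye rescue, which keeps the patient to Month 20. Wear-off after the Week 32 implant cannot bring exit before Month 19.4.

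A reader might also infer that the lost time is when the polymer is still degrading. Exit is permitted only from 12 months after the last administration, and Protocol 1.3 expects more than 75% degradation within about 12 months, so that window is covered.

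Other points stand in part:
- Protocol 3 allows early exit only where the investigator has no safety concerns. That would hold back some of the patients of most interest, although 8.8 does not repeat the condition.
- Skipping Month 14 or 18 does not erase events, since Protocol 9.1.1 has each visit ask about the time since the last one.
- In the earlier clinical study most adverse events came within 2 days of administration (Protocol 1.3.3), so the overall TEAE percentage should be affected much less than late events.
- The tables are descriptive, with no formal between-arm test in the readable text. Study duration, administration counts and disposition by cycle are already shown by group, so unequal follow-up would be visible.
- Parts of SAP 11 are blacked out and table specifications are in a separate document, so an adjusted analysis may exist.

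None of this supplies, in readable text, an estimate of late risk that allows for time observed, or a by-period home for late events in patients with fewer than three injections.

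**Conclusion.** The point holds in a direction-neutral form. Observation after Week 52 depends on both-eye rescue and missed administrations, and the readable SAP reports whole-study TEAEs with no allowance for it. Under the assumed exit shares, events arising after Week 52 show at about 92% to 69% of their true value in the arm concerned. In the unequal-exit examples the crude ratio between arms moves about 14% to 16% either way from the true one.

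These figures assume exit at the earliest permitted date, a constant late hazard and non-informative exit; later or rarer exits shrink them. A bias toward the implant is possible but not shown. In absolute terms the effect is small, about 1 to 3 patients per 200 at a 5% late risk, so this is an inexpensive improvement to the safety reporting and leaves the efficacy conclusions untouched.

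**What to change.** In SAP 11.0 and 11.1:

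1. Keep the crude whole-study TEAE percentages.
2. Add a Day 1 to Week 52 TEAE table by arm as the comparison over a common length of follow-up. Note that patients rescued in both eyes attend fewer visits in this period too (Protocol 5.6.1).
3. For Week 52 to Month 20, report by arm, for all treated patients whatever their number of injections, the number in follow-up. Add period-specific rates per time at risk, or Kaplan-Meier estimates of time to first event, for overall, ocular and treatment-related TEAEs. Do not rely on a single whole-study patient-year rate.
4. Widen the extended safety follow-up period in SAP 11.0 to patients with fewer than three injections, and state where their events after the truncated Cycle 1 or 2 window are reported.
5. Reconcile Protocol 3 with Protocol 8.8 on whether early exit requires the absence of safety concerns.

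If the redacted text or the table specifications already contain item 3, a cross-reference is enough.

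The cost is SAP wording and a few tables from data already collected. The added estimates still assume that exit is non-informative, and they do not correct for fewer examinations in patients excused from visits.
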